9.3 Withdrawal and Discontinuation

Any subject may voluntarily withdraw (ie, reduce the degree of participation in the study) consent for continued participation and data collection. The reason for withdrawal will be recorded on the End of Study eCRF. Assessments to be done at the termination visit (including in cases of withdrawal or discontinuation) are described in [Section 10.6](#) and [Section 20.2](#).

Discontinuation (ie, complete withdrawal from study participation) may be due to dropout (ie, active discontinuation by subject) or loss to follow-up (ie, discontinuation by subject without notice or action). Additionally, the investigator and sponsor have the discretion to discontinue any subject from the study if, in their judgment, continued participation would pose an unacceptable risk for the subject.

Subjects also will be withdrawn from treatment or discontinued from further study participation for the following reasons:

- Failure to achieve at least a PASI 50 response at Week 25
- The subject becomes pregnant. IP exposure will be discontinued. Attempts will be made to follow the subject through completion of the pregnancy and up to 1 year post-delivery, if feasible. The investigator will record a narrative description of the course of the pregnancy and its outcome
- AEs/SAEs that in the investigator or sponsor opinion, poses an unacceptable risk for continued dosing in the subject
- The subject is determined by the sponsor or investigator to be noncompliant with administration of IP, despite evidence of retraining of the subject. The subject will be discontinued from further participation in the study
- Participation in another clinical study involving an IP during the course of the study

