10.6 Subject Completion/Discontinuation

A subject is considered to have completed the study when he/she ceases active participation in the study because the subject has, or is presumed to have, completed all study procedures according with the protocol (with or without protocol deviations).

Reasons for completion/discontinuation will be reported on the Completion/Discontinuation eCRF, including:

- Completed
- Screen failure
- AE (eg, death),
- Discontinuation by subject (eg, lost to follow-up [defined as 3 documented unsuccessful attempts to contact the subject], dropout)

- Physician decision (eg, pregnancy)
- Progressive disease
- Non-compliance with IP/protocol deviation(s), recovery, study terminated by sponsor
- Other (reason to be specified by the investigator, eg, technical problems)

Regardless of the reason, all data available for the subject up to the time of completion/discontinuation should be recorded on the appropriate eCRF.

Every effort will be made to have discontinued subjects complete the study completion/termination visit. If the completion/termination visit is done as an additional, unscheduled visit, the assessment results shall be recorded with the completion/termination visit. If a subject terminates participation in the study and does not return for the completion/termination visit, their last recorded assessments shall remain recorded with their last visit. The reason for discontinuation will be recorded, and the data collected up to the time of discontinuation will be used in the analysis and included in the clinical study report.

If additional assessments are required, the assessments shall be recorded separately. Assessments to be done at the termination visit (including in cases of withdraw or discontinuation) can be found in [Table 1](#) and [Table 2](#).

After the discontinuation visit, if the subject agrees, a follow-up visit performing the same assessments as the Week 52 visit should be conducted 5 weeks after last IP dose.

In the event of subject discontinuation due to an AE, clinical and/or laboratory investigations that are beyond the scope of the required study observations/assessments may be done as part of the evaluation of the event. These investigations will take place under the direction of the investigator in consultation with the sponsor, and the details of the outcome may be reported to the appropriate regulatory authorities by the sponsor.

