13.3 Handling of Missing, Unused, and Spurious Data

Non-Responder Imputation (NRI) for Clinical Response: Subjects will be considered as non-responders for the NRI analysis if they do not meet the clinical response criteria for categorical responses (PASI50, PASI75, PASI90, sPGA) at a time point of interest (Week 16). All non-responders at Week 16, as well as all subjects who discontinue study treatment prior to Week 16 for any reason, will be defined as non-responders for the NRI analysis for all categorical PASI and sPGA analyses at the time point of interest.

Modified Baseline Observation Carried Forward (mBOCF): The continuous efficacy and health outcome variables will be based on a modified baseline observation carried forward (mBOCF) approach. For subjects who discontinue the study treatment due to AE, the baseline observation will be carried forward to the corresponding time point for evaluation. For subjects who discontinued the study treatment due to any other reason, the last non-missing observation before discontinuation will be carried forward to the corresponding time point for evaluation. Randomized subjects without at least 1 post-baseline observation will not be included for evaluation with the exception of subjects who discontinued the study treatment due to AE.

Mixed Models for Repeated Measures (MMRM): As a supportive analysis, continuous endpoints will be imputed based on mixed-effects model repeated measures (MMRM) for the ITT population⁸. Categorical endpoints derived from continuous measures will be derived from the imputed continuous measure.

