5.2 Handling of Missing, Unused, and Spurious Data

Efficacy Measures

Imputation for missing PASI scores will be limited to assessments performed from the Week 0 to Week 16 visits. NRI imputation will be applied to data beyond the Week 16 visit for subjects who continued to receive M923 after Week 16 and those originally administered EU RPP and re-randomized at Week 16.

The primary analysis will be based on the non-responder imputation (NRI) method. Sensitivity analyses for PASI75, PASI50, and PASI90 will include modified baseline observation carried forward (mBOCF) and mixed model for repeated measures (MMRM) methods. This section describes the details of each of the imputation procedures.

Non-Responder Imputation (NRI) for Clinical Response: For binary endpoints PASI75, PASI50, PASI90, and sPGA, the primary analysis will be based on NRI.

Subjects will be considered as non-responders at a time point of interest for the NRI analysis in any of the following situations:

- No valid PASI score at baseline.
- No valid post-baseline PASI score for any reason at the time point of interest.
- No improvement in PASI score from baseline or an improvement of less than 50%, 75%, and 90% for response measures PASI50, PASI75 and PASI90, respectively, at the time point of interest. No improvement in sPGA of clear or almost clear at the time point of interest.

Modified Baseline Observation Carried Forward (mBOCF): As a supportive analysis, continuous PASI scores will be imputed based on a modified baseline observation carried forward (mBOCF) approach. Categorical endpoints will be derived from the imputed continuous measure.

Missing values at a time point of interest will be imputed as follows:

- For subjects who discontinue the study treatment due to AE(s) or death before the Week 16 visit, the baseline observation will be carried forward to the corresponding time point for evaluation (BOCF).
- For subjects who discontinue the study treatment due to any other reason other than AE or death before the Week 16 visit, the last non-missing observation before discontinuation will be carried forward to the corresponding time point for evaluation (LOCF).
- For subjects who complete the study treatment through the Week 16 visit, the last non-missing observation will be carried forward to the corresponding time point for evaluation (LOCF).

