7. EFFICACY EVALUATION

All efficacy measures will be summarized and evaluated utilizing the PP Analysis set and repeated using the mITT Analysis set as sensitivity analysis. Listings will be presented using the ITT Analysis set,

For the Primary and Secondary analysis, visit windowing conventions will occur at Week 16 for the purpose of equivalence testing. Based on a target day of 113, a lower bound of window (day) 103 and an upper bound of window (day) 123 will be used.

If more than one visit falls within the same visit Week 16 window, the data from the visit closest to the target day will be used for the visit summary. If two visits within the same visit window are equidistant from the target day, the data from the later visit will be used for the protocol specified visit.

Data will be listed and summarized with descriptive statistics, by randomized treatment group. Further details are provided in the following sub-sections.

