7.1 Analysis of Primary Efficacy Outcome Measure

The primary efficacy objective will be met by demonstrating that subjects randomized to M923 (Arm A) and those randomized to EU RPP (Arm B) have a statistically equivalent PASI75 response rate at Week 16 (Visit 7).

The primary efficacy variable is the PASI75 response rate at Week 16 (Visit 7). A PASI75 responder at Week 16 is defined as a subject who achieves at least 75% improvement in PASI score from baseline at Week 16. The primary efficacy analysis is a test for equivalence between M923 and EU RPP groups (as randomized) and will be performed on the PP analysis set. Where missing data occurs, the NRI method (see [Section 5.2](#)) will be used to impute values.

The primary efficacy objective will be met by demonstrating that subjects randomized to M923 (Arm A) and those randomized to EU RPP (Arm B), have a statistically equivalent PASI75 response rate at Week 16 (Visit 7).

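### The SAP's non-responder list drops the protocol's rule on stopping treatment before Week 16, no ITT efficacy repeat is specified, and SAP 5.5 declares neither change

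*SAP*

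**What the plan says.** **Non-responder rule.** Protocol 13.3 has two limbs for the categorical PASI and sPGA endpoints. Subjects who miss the response criteria at Week 16 are non-responders, "as well as all subjects who discontinue study treatment prior to Week 16 for any reason, will be defined as non-responders". SAP 5.2 opens its list with "Subjects will be considered as non-responders at a time point of interest for the NRI analysis in any of the following situations" and gives three kinds of situation: no valid baseline PASI, "No valid post-baseline PASI score for any reason at the time point of interest", and improvement below the threshold (or sPGA not clear or almost clear). Stopping treatment is not in the list, although the mBOCF rules in the same section do turn on it.

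**Week 16 data.** SAP 7 sets a target of day 113, with "a lower bound of window (day) 103 and an upper bound of window (day) 123 will be used". If several visits fall in the window, "the data from the visit closest to the target day will be used for the visit summary". SAP 7.1 labels the primary variable as Visit 7.

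**Populations.** Protocol 13.4.3 repeats the primary analysis on ITT with NRI, mBOCF and MMRM, and 13.4.4.1 repeats the secondary efficacy analyses on ITT. SAP 7, 7.2 and 7.3 name only PP and mITT, with ITT kept for listings. Under SAP 4.3, mITT requires post-baseline data on at least one efficacy endpoint.

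**Declared changes.** SAP 5.5 reports no significant change. It mentions a clarified PP definition and presents mITT as an extra supplementary set for the primary analysis.

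**The concern.** The two documents can give the same subject different Week 16 outcomes, on the endpoint and in the population that decide equivalence. Under the protocol, stopping early is itself a failure. Under the SAP, only a missing or insufficient score is.

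Separately, the protocol promises a check on the PP result in all randomised subjects. No SAP section specifies that comparison, while SAP 5.5 reads as though the protocol's analyses still stand with mITT added. SAP 5.1 says the SAP holds all the methods needed for both study reports, so no other document can be expected to supply it.

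**Working it through.** **1. Who is classified differently.** Early stoppers without a Week 16 score are non-responders under both documents. The gap is limited to early stoppers with a valid PASI in days 103-123. Taking last-dose day = 7 × week + 1, there are three routes:

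- *Off treatment, still in the study.* Protocol 9.3 separates the two: "Subjects also will be withdrawn from treatment or discontinued from further study participation for the following reasons". Such a subject could attend Visit 7.
- *Termination visit.* Protocol 10.6 says "Every effort will be made to have discontinued subjects complete the study completion/termination visit", and under 10.3.3 that visit includes PASI. With a last dose at Week 13 (7 × 13 + 1 = day 92), a termination visit on days 103-109 lies inside the SAP window but before Visit 7's own window of 113 ± 3 = days 110-116.
- *Follow-up five weeks after the last dose* (protocol 10.6; PASI is included under 10.3.4). With a last dose at Week 11 (7 × 11 + 1 = day 78), 78 + 35 = day 113, the exact target day.

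**2. Whether another SAP rule closes the gap.** SAP 8 keeps the early withdrawal visit separate, but for safety only. SAP 5.2 sets aside unscheduled assessments, but only under Other Outcome Measures and for descriptive statistics. Stopping treatment is not in itself a listed ground for PP exclusion (protocol 13.2, SAP 6.7).

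**3. Size of the classification gap.** The documents do not give the number of affected subjects. Planned loss by Week 16 is 516 − 490 = 26, about 13 per arm. One subject moves an arm's rate by 1/258 = 0.39 points.

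The chance of declaring equivalence when the true difference sits at the margin was found by exact binomial enumeration with an unstratified Newcombe interval. Assumptions: reference rate (578 + 86)/(814 + 108) = 664/922 = 72.0%; M923 rate lower by 15 points (95% interval, EU) or 18 points (90% interval, US); one expected recoded subject adds 1/n to that arm's rate.

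| Expected recoded subjects | EU, 258/arm | US, 258/arm | EU, 245/arm | US, 245/arm |
|---|---|---|---|---|
| none | 2.57% | 5.03% | 2.66% | 5.09% |
| one, M923 only | 3.18% | 6.08% | 3.30% | 6.19% |
| one in each arm | 2.57% | 5.05% | 2.64% | 5.12% |
| one, reference only | 2.06% | 4.14% | 2.11% | 4.18% |

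One subject can change the verdict only near the boundary. With the reference at 186/258:

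- EU, 95% interval: 167 M923 responders give −15.26 to 0.66 (fail); 168 give −14.86 to 1.03 (pass).
- US, 90% interval: 156 give −18.32 to −4.78 (fail); 157 give −17.93 to −4.41 (pass).

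Away from the boundary there is ample room. With equal true rates of 71%, 258 per arm and 13 subjects recoded in one arm only, the difference moves by 13/258 = 5.04 points and the 95% interval goes from (−7.8, 7.8) to (−2.6, 12.6), still inside 15.

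**4. Size of the ITT to mITT change under NRI.** Removing one M923 non-responder who has no post-baseline data shifts the difference by 186/257 − 186/258 = +0.28 points, or 164/257 − 164/258 = +0.25 points at a lower rate. One removed from the reference arm shifts it by about −0.28, and one from each arm by about 0.

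**The case against.** The strongest reply is that the gap is very narrow. An affected subject must stop early, have a score in the window, reach PASI75 and stay in PP. Use of prohibited medication, which leads to discontinuation, is also a listed ground for PP exclusion, and other deviations are judged case by case. No section explicitly schedules Visit 7 for a subject off treatment. Protocol 10.6 records an unscheduled termination visit under the termination label, the five-week follow-up is optional, and SAP 7.1 names Visit 7. The multiple-visit rule may have been written only for Visit 8, whose days 117-123 also lie inside the window.

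This limits the likely count but does not close the gap. SAP 7 assigns Week 16 data by day and does not restrict the choice to Visit 7, so the visit labels do not settle the matter. Case-by-case PP review may remove some early stoppers, but no stated rule removes them as such.

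The illustrated count of one is assumed, and the calculation is unstratified whereas the SAP stratifies by region. Both are fair limits on the figures.

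On populations, ITT is only a sensitivity analysis. PASI is scored from Week 1, so mITT should lose few subjects. The protocol's own mBOCF rule already leaves out most subjects without post-baseline data. That stands: the loss matters mainly under NRI.

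SAP 5.5 has a redaction and a sentence that breaks off, so the statement that it declares neither change applies to the visible text. Those places concern health outcomes and safety periods, where these changes would not be expected.

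**Conclusion.** The concern holds. The SAP omits a stated responder rule of the protocol and specifies no ITT repeat of the efficacy analyses, and the visible text of SAP 5.5 declares neither. It should be fixed.

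The numerical effect is probably small and has no fixed direction. It depends on an unknown number of early stoppers with in-window scores and on how they split between arms. Under the assumptions above, one such subject in a single arm changes the pass rate at the margin by about 0.5 to 0.6 points (EU) or 0.9 to 1.1 points (US), and one in each arm leaves it almost unchanged. The ITT omission does not affect the primary error rate. What is lost is the all-randomised comparison, which matters mainly under NRI.

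**What to change.** 1. In SAP 5.2, add to the non-responder list, for the Week 16 PASI and sPGA analyses only, any subject who stopped study treatment before Week 16, whatever the reason.
2. In SAP 7.3, add the ITT population with NRI, and with mBOCF and MMRM as protocol 13.4.3 states. Add ITT to SAP 7 and to the response-rate analyses in SAP 7.2. Keep mITT as supplementary.
3. In SAP 5.5, declare any departure that remains, including the use of mITT for secondary measures.

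The cost is a few lines of SAP wording and one more set of tables. ITT response rates under NRI will be slightly lower than the mITT rates, because randomised subjects without post-baseline data count as failures.

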13.4 Methods of Analysis

In general, all efficacy, safety, PK, and immunogenicity variables will be summarized using descriptive statistics. Continuous variables will be summarized by sample size, mean, standard deviation, median, minimum, and maximum. Categorical variables will be summarized in frequency tables (n, frequencies, and percentages). Individual subject data will be presented in listings.

The study consists of a treatment period of 48 weeks and subsequent safety follow up. The analysis of primary outcome will use data from the first 16 weeks.

The default significant level will be (5%); confidence intervals will be 95% and all tests will be 2-sided, unless otherwise specified in the description of the analyses. Details of the statistical analysis will be specified in the Statistical Analysis Plan (SAP), which will be finalized prior to treatment assignment unblinding. The SAP will contain the details of the missing data modeling, including model specification, the analysis of the secondary and pharmacokinetic endpoints, and the presentation of safety data.

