- For subjects who do not have any post-baseline data and did not discontinue the study treatment due to AE(s) or death prior to the Week 16 visit, missing values will not be imputed and subjects will be excluded from the analysis.

Mixed Models for Repeated Measures (MMRM): As a supportive analysis, continuous PASI scores will be imputed based on mixed-effects model for repeated measures (MMRM). Categorical endpoints will be derived from the imputed continuous measure. The MMRM model will use PASI data from the Week 0 to Week 16 visits and will

include covariates for baseline PASI score (continuous), treatment group (A, B), visit (Week 1, 4, 8, 12 and 16), region (North America, Western Europe, or Eastern Europe/Asia), and the treatment-by-visit interaction. An unstructured variance-covariance matrix will be estimated. If the procedure fails to converge a heterogenous Toeplitz structure will be used for the variance-covariance matrix. The Kenward-Roger method will be used for estimating degrees of freedom.

Observed Case: As a supportive analysis for PASI scores, the observed data, with no imputation for missing data, will be summarized with descriptive statistics.

Adverse Events

At database lock and before the unblinding occurs, all AEs will be checked for missing causality assessment and/or severity grades. Any missing cases, will be reviewed by pharmacovigilance monitor or designee and appropriate data handling decisions will be provided on case by case.

Other Outcome Measures

Unless otherwise specified, for all other outcome measures, descriptive statistics will be presented in tables, with no action to handle missing data (observed case). Subjects who withdraw prior to the last planned observation in the study period will be included in the analyses up to the time of withdrawal.

Extra measurements (such as unscheduled or repeat assessments) will not be included in the descriptive statistics, but will be included in subject listings.

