7.3 Sensitivity Analyses

For the primary efficacy measure, PASI75 response rate at the Week 16 visit, sensitivity analyses will include repeating the primary analysis using:

- mITT population with NRI method for missing data,

- PP and mITT populations with mBOCF for missing data, and
- PP and mITT populations with MMRM for missing data.

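### Read plainly, the MMRM sensitivity analysis cuts a model-filled PASI at the responder threshold and analyses it as observed; the effect is small at the planned 5% loss, but multiple imputation should replace it

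*SAP*

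**What the plan says.** SAP 5.2 names non-responder imputation (NRI) as the primary method and adds mBOCF and MMRM as sensitivity methods for PASI75, PASI50 and PASI90. Under MMRM, "continuous PASI scores will be imputed based on mixed-effects model for repeated measures (MMRM). Categorical endpoints will be derived from the imputed continuous measure". The model uses PASI from Weeks 0 to 16, with baseline PASI, treatment, visit, region and treatment-by-visit terms, an unstructured covariance and Kenward-Roger degrees of freedom.

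SAP 7.3 says that for PASI75 at Week 16 "sensitivity analyses will include repeating the primary analysis using" a list of options, one of which is "PP and mITT populations with MMRM for missing data". The primary analysis being repeated is the one in SAP 7.1.1: the difference in response rates with a Newcombe score interval stratified by region, read against 18% at 90% confidence (FDA) and 15% at 95% confidence (EMA).

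Protocol 13.3 describes the same step: "continuous endpoints will be imputed based on mixed-effects model repeated measures (MMRM) for the ITT population", and then "Categorical endpoints derived from continuous measures will be derived from the imputed continuous measure". Protocol 13.4 leaves the rest to the SAP: "The SAP will contain the details of the missing data modeling, including model specification". SAP 5.2 does specify the model. It does not say how a missing score is generated from it, how many times, or how the results are combined. It also does not say whether the prediction uses the subject's own earlier scores.

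**The concern.** There are two separate problems if each missing score is filled once with its predicted mean.

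- **The rate.** Whether a predicted mean lies below the 25%-of-baseline line is not the same as the probability that the subject's score does. A subject with a 45% chance of response, whose predicted mean falls just short, counts as 0 rather than 0.45. Predicted means also pull towards the centre, so the error is largest for an extreme threshold such as PASI90.
- **The interval.** The Newcombe interval is a complete-data binomial interval. It counts filled-in subjects as if they had been seen. Kenward-Roger acts on the MMRM fit and does not reach that interval.

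The stake is the credibility of the sensitivity analysis. NRI has two inferential alternatives in SAP 7.3, mBOCF and MMRM, and mBOCF is also a single fill-in. On the plain reading, no planned analysis carries imputation uncertainty. In an equivalence trial, an interval that is too narrow errs towards the claim.

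**Working it through.** **1. Planned missing share.** The Protocol synopsis gives 516 randomised to yield 490 completing Week 16. The loss is 26/516 = 5.04%, and 490/0.95 = 515.8, which rounds up to 516. The 5% is inferred from these two figures, because the power assumptions are redacted.

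**2. Response rate.** Protocol 13.1.1 gives 578/814 and 86/108. The crude pooled rate is 664/922 = 72.0%, used here for both arms.

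**3. Ceiling on the interval error.** Compare the Newcombe half-width with 258 per arm (all counted as observed) and with 245 per arm (missing subjects carry no information). It is unstratified here, for simplicity.

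Wilson limits: [p + z²/2n ± z√(p(1−p)/n + z²/4n²)] / (1 + z²/n). With equal rates, the Newcombe half-width is √[(p − L)² + (U − p)²].

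- n = 258, 95%: L = 0.6623, U = 0.7713, half-width √(0.0577² + 0.0513²) = 7.72 points.
- n = 245, 95%: L = 0.6607, U = 0.7725, half-width √(0.0593² + 0.0525²) = 7.92 points.
- At 90%: 6.48 and 6.65 points.

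7.92/7.72 = 1.026, so the wider interval is about 2.6% wider, a gap of 0.2 point. Earlier visits carry some information, so a proper interval should lie at about or between the two values. At 10% missing, √0.90 = 0.949, a ceiling of about 5%.

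**4. Bound on the rate error.** Shift in an arm's rate = missing share × (imputed rate − true rate among the missing). At 5.04% missing, the extremes are −2.5 to +2.5 points if half of the missing truly respond, and −3.6 to +1.5 points if 71% do.

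**5. Simulated whole trials.** Assumptions: 258 per arm, true PASI75 about 71% in both arms, visits at Weeks 1, 4, 8, 12 and 16, and a normal repeated-measures model with unstructured covariance and no region term. Missing scores take the conditional mean and are then cut at 25% of baseline. The PASI course, correlations and dropout models are assumed, not taken from the documents.

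| Missing (arm A / arm B) | Shift in arm rates (points) | Shift in difference (points) | Coverage of 95% CI |
|---|---|---|---|
| 5% / 5%, completely at random | 0.1 | under 0.1 | 95.3% |
| 5% / 5%, depends on earlier PASI (two runs) | 0.2–0.3 | under 0.1 | 94.5%, 95.3% |
| 5% / 5%, early dropout | 0.3 | under 0.1 | 94.6% |
| 3% / 7%, depends on earlier PASI | 0.2 / 0.4 | 0.2 | 95.0% |
| 3% / 7%, early dropout | 0.2 / 0.3 | 0.2 | 94.9% |
| about 17% in each, depends on earlier PASI | 1.5–1.6 | 0.1 | 93.5% |

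At about 5% missing, the spread of the estimated difference was 1.00 to 1.04 times what the interval implied; at 17% it was 1.06. The 17% row has 400 trials, so its coverage has a simulation error of √(0.935 × 0.065/400) = 1.2 points, and 93.5% is only a hint of undercoverage.

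**6. A harsher case.** Suppose every missing subject is a poor-course dropout. In one assumed PASI course, such subjects truly responded in 48% but were imputed at 22% (dropout after Week 4), or 45% against 31% (after Week 8). At 5% missing this moves an arm by 0.05 × 26 = 1.3 or 0.05 × 14 = 0.7 points. A log-normal course gave up to 61% against 33%: 0.05 × 28 = 1.4 points. If 3% and 7% were missing, the 26-point gap would move the difference by 0.26 × 4 = about 1.0 point.

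**7. PASI90.** Under random dropout in the log-normal course, a true PASI90 rate of 37% among the missing was imputed as 0 to 21%.

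**8. Would drawing values help?** In the balanced 5% trials of step 5 where dropout depended on earlier PASI, the true response among the missing was 50%. The thresholded mean gave 44%, and random draws from the same normal model on raw PASI gave 41%. Draws on the log scale recovered the truth in the log-normal course, which is so by construction.

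**The case against.** The best reply has four parts.

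- **Single imputation is not stated.** A reader might infer that the SAP prescribes one predicted value per missing score. It does not say so, and it does not rule out multiple imputation. That is correct, and the point is worded accordingly. But if multiple imputation was meant, the analysis cannot be run as written, because the draws, seed, scale and pooling are all absent. Either reading needs the same edit.
- **Nothing decisive hangs on it.** A reader might infer that the equivalence claim is at risk. The documents do not support that: equivalence is declared on the NRI analysis of the PP set, the MMRM analysis is labelled supportive, and 0.2 point is small against 15 and 18. This stands. Similar shifts in both arms also largely cancel in the difference.
- **Missingness may be below 5%.** The mITT set requires post-baseline data on at least one efficacy endpoint. The Week 16 window (days 103 to 123, SAP 7) also takes in the Week 17 visit on day 120, when PASI is scored again. This stands, although the actual missingness is not in the documents.
- **Multiple imputation is not a cure by itself.** Normal draws on raw PASI were further from the truth than the thresholded mean, log PASI is undefined at a score of 0, and Rubin's rules do not reproduce the stratified Newcombe interval. All three stand and shape the fix.

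None of these turns the thresholded mean into an estimate of the response rate, or puts imputation uncertainty into the interval.

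**Conclusion.** The concern holds, with single imputation as an inferred reading and a small size at the planned loss. At 5% missing and a 72% rate, the interval that allows for the loss is at most about 2.6% wider than the one the plan would report. An arm's PASI75 rate moves by about 0.1 to 1.4 points: the low end comes from mixed dropout in whole-trial simulations, the high end from assuming that all dropouts have a poor course. The arm difference moved by at most about 0.2 point in the simulated trials, and could move by about 1 point if poor-course dropout were 3% in one arm and 7% in the other. PASI90 is affected more than PASI75.

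All rate figures rest on assumed PASI courses and dropout patterns; only the interval ceiling and the bounds in step 4 follow from the documents' own counts with the 72% rate, or the stated response among the missing, put in. The 572 actually randomised would narrow every interval by a factor of about √(516/572) = 0.95. The primary NRI result is unaffected. The change is worth making because this analysis is meant to show whether missing data matter, and its error grows as they do.

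**What to change.** In SAP 5.2, replace the MMRM fill-in with multiple imputation, keeping its place as a supportive analysis in SAP 7.3:

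- Impute missing PASI through Week 16 from a repeated-measures model with the same covariates, and state that it conditions on the subject's own earlier scores.
- Use a scale suited to skewed PASI, for example log(PASI + a stated constant), so that a score of 0 is allowed. Do not draw on raw PASI.
- State the number of imputations (for example 50) and the seed.
- Derive PASI50, PASI75 and PASI90 in each completed data set.
- Combine the region-stratified risk differences by Rubin's rules, or use a stated multiple-imputation version of the Newcombe interval.
- Report the 90% interval against 18% and the 95% interval against 15%.

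If multiple imputation was already intended, the same list supplies what the text lacks.

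The cost is a paragraph of SAP text and standard SAS procedures. The supportive interval becomes slightly wider, and with Rubin's rules it is no longer exactly the primary Newcombe method, which the SAP should say. No change to the primary analysis, the sample size or data collection is needed.
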